9.3.3. Fasting Glucose and Lipids

Analyses of fasting glucose and lipid parameters (LDL-c, HDL-c, VLDL-c, total cholesterol, triglycerides) will be carried out using an ANCOVA model at each visit with change (and percent change [except for glucose]) from baseline as the dependent variable including treatment group as a fixed effect and baseline as a covariate. The same analysis will be carried out using change from baseline as the dependent variable. The estimates of least-square (LS) means, standard errors, and 90% and 95% CIs will be presented by treatment group. Estimates of the LS mean difference between pooled TERN-101 (All TERN-101) and pooled placebo, and each pairwise comparison between pooled placebo and each active dose of TERN-101, will be presented with the associated standard error of the difference, and 90% and 95% CI of the difference, the standard error of the difference, and 90% and 95% CI of the difference will be presented.

Figures of mean (\pm SD) LDL and HDL values will be presented over time by treatment group. In addition, figures of LS mean (\pm SE) changes from baseline will be presented over time by treatment group.

9.3.4. Shifts in CTCAE Grade

Shifts in CTCAE grade of laboratory tests will be presented from baseline to worst post-baseline value and at each post-baseline visit. Summaries will present the number and percentage of patients with shifts in laboratory grade by treatment group. Denominators for percentages will be the number of patients with non-missing data at the specific assessment and baseline.

LDL-c will be summarized separately using the categories defined in Section 9.3.1.

Some lab tests include additional clinical criteria which cannot be determined programmatically. Table 11 below specifies the grade with clinical criteria in italics. The text in italics will not be considered when assigning grades programmatically.

Table 11: CTCAE Laboratory Tests with Clinical Criteria

| |
|---|
| Bicarbonate (Blood bicarbonate decreased): |
| 
Grade 1: <LLN and no intervention initiated. |
| Prothrombin Time (PT)/International Normalized Ratio (INR) (INR increased): |
| 
Grade 1: >1.2 - 1.5; >1 - 1.5 x baseline if on anticoagulation; monitoring only indicatedGrade 2: >1.5 - 2.5; >1.5 - 2.5 x baseline if on anticoagulation; dose adjustment indicatedGrade 3: >2.5; >2.5 x baseline if on anticoagulation; bleeding |

eGFR (Chronic Kidney Disease):

- Grade 4: $<15 \text{ ml/min/1.73m}^2$; *dialysis or renal transplant indicated*

Glucose (Hypoglycemia):

- Grade 4: $<30 \text{ mg/dL}$; $<1.7 \text{ mmol/L}$; *life-threatening consequences; seizures*

Potassium (Hypokalemia)

- *Grade 2: Symptomatic with $<LLN - 3.0 \text{ mmol/L}$; intervention indicated*
- Grade 3: $<3.0 - 2.5 \text{ mmol/L}$; *hospitalization indicated*
- Grade 4: $<2.5 \text{ mmol/L}$; *life-threatening consequences*

Potassium (Hyperkalemia):

- Grade 2: $>5.5 - 6.0 \text{ mmol/L}$; *intervention initiated*
- Grade 3: $>6.0 - 7.0 \text{ mmol/L}$; *hospitalization indicated*
- Grade 4: $>7.0 \text{ mmol/L}$; *life-threatening consequences*

Sodium (Hyponatremia):

- Grade 2: $125-129 \text{ mmol/L}$ and *asymptomatic*
- Grade 3: $125-129 \text{ mmol/L}$ *symptomatic*; $120-124 \text{ mmol/L}$ regardless of symptoms
- Grade 4: $<120 \text{ mmol/L}$; *life-threatening consequences*

Sodium (Hypernatremia):

- Grade 2: $>150 - 155 \text{ mmol/L}$; *intervention initiated*
- Grade 3: $>155 - 160 \text{ mmol/L}$; *hospitalization indicated*
- Grade 4: $>160 \text{ mmol/L}$; *life-threatening consequences*

Albumin (Hypoalbuminemia):

[figure not shown]
- *Grade 4: Life-threatening consequences; urgent intervention indicated*

9.3.6. COVID-19

SARS-CoV-2 test for active infection and SARS-CoV-2 antibody test results, central and local labs, will be presented in a by-patient listing. A separate listing for central and local laboratory normal ranges, by lab test, lab parameter, sex, and age, will be presented.

At study initiation, the EDI Epitope assay was used for SARS-CoV-2 antibody testing. During the study, the EDI Epitope assay was discontinued. Where possible, samples were re-assayed using the Abbott assay. Both assay results are included in the central laboratory results. If both results are available, the Abbott assay results will be reported instead of the EDI Epitope assay results.

The number and percent of patients with any positive COVID-19 test result (i.e., either test method) and separately by test method at baseline and at any post-baseline visit will be presented by treatment group. Antibody test results will be further separated by IgG and IgM.

11. CHANGES TO PROTOCOL PLANNED ANALYSES

The Enrolled Analysis Set was renamed to Screened Analysis Set.

The Safety Analysis Set was changed to remove 'randomized', as per regulatory guidance, any patient who receives study drug, regardless of whether the patient was randomized or not, will be included in analyses. In addition, as all patients are evaluated for safety post dose (e.g. AEs), the specification of 'and have post dose safety data' was removed.

Study endpoints were further clarified.

13. APPENDICES

[REDACTED]

[REDACTED]

[REDACTED]

[REDACTED]

[REDACTED]

APPENDIX 3. IMPUTATION RULES FOR MISSING OR PARTIAL DATES FOR ADVERSE EVENTS AND CONCOMITANT MEDICATIONS

| Date | Situation | Imputation Rule |
|---|--|--|
| Start Date | Only month and year are known and month and year are prior to first dose date | Use the last day of the month |
| | Only month and year are known and month and year are the same as first dose date | Use the first study drug administration date |
| | Only month and year are known and month and year are after first dose date | Use the first day of the month |
| | Only year is known and year is before first dose date | Use Dec 31 of that year |
| | Only year is known and year is same as first dose date | Use the first study drug administration date |
| | Only year is known and year is after first dose date | Use Jan 1 of that year |
| | Entire date is missing | Use the first study drug administration date |
| | The estimated start date is after a complete or imputed AE stop date | Use the first day of the month of the AE stop date |
| Stop/End Date | Only month and year are known and month and year are prior to last dose date | Use the last day of the month |
| | Only month and year are known and month and year are the same as last dose date | Use the last dose date |
| | Only month and year are known and month and year are after last dose date | Use the last day of the month |
| | Only year is known and year is before last dose date | Use Dec 31 of that year |
| | Only year is known and year is same as last dose date | Use the last study drug administration date |
| | Only year is known and year is after last dose date | Use Dec 31 of that year |
| | Entire date is missing | Use the last study drug administration date |
| | The estimated stop date is before a complete or imputed AE start date | Use the last day of the month of the AE start date |
| AE = adverse event, Dec = December, Jan = January | | |

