9.2. Adverse Events

Adverse event (AE) verbatim terms on eCRFs will be mapped to preferred terms (PT) and system organ classes (SOC) using MedDRA. AE severity will be categorized using the National Cancer Institute Common Terminology Criteria for Adverse Events (NCI CTCAE, Version 5).

All AEs will be listed, but summaries will be restricted to TEAEs, defined as any AE with a start date on or after the date of first administration of study drug through 30 days after the last administration of study drug or through the Follow-Up Period (Week 16). Related SAEs after Week 16 will be considered TEAEs. If it cannot be determined whether an AE is treatment emergent due to a partial onset date, then it will be counted as such. Methodology for imputation of partial AE start and stop dates is described in [Appendix 2](#). Each summary will be displayed by treatment group.

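### SAP Appendix 3: two date-consistency rows can both apply to one adverse event and no visible text orders them, so an imputed stop date can override a recorded onset month

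*SAP*

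**What the plan says.** Appendix 3 of the SAP gives separate start-date and stop-date rows. These matter here:

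- Start, month and year only: "Only month and year are known and month and year are after first dose date | Use the first day of the month".
- Stop, nothing recorded: "Entire date is missing | Use the last study drug administration date".
- Stop, year only: "Only year is known and year is same as last dose date | Use the last study drug administration date".
- Start consistency row: when "The estimated start date is after a complete or imputed AE stop date", the action is "Use the first day of the month of the AE stop date".
- Stop consistency row: when "The estimated stop date is before a complete or imputed AE start date", the action is "Use the last day of the month of the AE start date".

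SAP section 9.2 bases treatment emergence on the start date: a TEAE is "defined as any AE with a start date on or after the date of first administration of study drug", through 30 days after the last dose or through the Follow-Up Period (Week 16). An event whose status cannot be settled because its onset date is partial is counted as a TEAE. Section 2.3.1 makes TEAE incidence a primary endpoint. Section 9.2.2 puts onset study day and event duration in the AE listings.

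**The concern.** The start consistency row treats an imputed stop date as equal to a reported one. A missing stop is set to the last dose date, which carries no information about the event. A recorded onset month does carry information, yet this row can overwrite it. It has no floor at the recorded month or at first dose.

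The mirror row is met by the same record and leads to a different answer. Two programmers could both follow the visible text and derive different onset dates. For most records only the listed onset day and duration are at stake. For a few early stoppers, a TEAE could drop out of a primary endpoint.

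Post-treatment onsets are expected, because the protocol (section 8.5.1) collects AEs through the Follow-Up Period. It requires follow-up to resolution or stabilization only for serious events (section 8.5.3), so a late non-serious event may have no stop date.

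**Working it through.** The plan gives no figure to reproduce. The check applies the Appendix 3 rows to dated examples and then to a grid of assumed dates.

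**Worked records** (illustrative dates)

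| Record | First dose | Last dose | Onset recorded | Stop recorded | Before consistency rows | Start row first | Stop row first |
|---|---|---|---|---|---|---|---|
| A | 14 Sep 2020 | 7 Dec 2020 | Jan 2021 | missing | 1 Jan 2021 / 7 Dec 2020 | 1 Dec–7 Dec 2020 | 1 Jan–31 Jan 2021 |
| B | 20 Jul 2020 | 12 Oct 2020 | Nov 2020 | 2020 | 1 Nov / 12 Oct 2020 | 1 Oct–12 Oct 2020 | 1 Nov–30 Nov 2020 |
| C | 8 Sep 2020 | 24 Sep 2020 | Oct 2020 | missing | 1 Oct / 24 Sep 2020 | 1 Sep–24 Sep 2020 | 1 Oct–31 Oct 2020 |
| D | 10 Mar 2021 | later | missing | Feb 2021 | 10 Mar / 28 Feb 2021 | 1 Feb–28 Feb 2021 | 10 Mar–31 Mar 2021 |

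- A and B are full courses (Day 1 to Day 85). With the start row first, an off-drug event is listed as on drug. In A the onset is Day 79 instead of Day 110, and the duration is 7 days (7 − 1 + 1) instead of 31 (31 − 1 + 1).
- C is an early stopper. With the start row first, the onset falls 8 − 1 = 7 days before first dose.
- D runs the other way. The recorded stop month shows that the event ended before dosing. The start row gives the right answer, and the stop row creates a false TEAE.
- If both rows are applied at once to the initial estimates, the onsets in A to C still move (A becomes 1 Dec 2020 to 31 Jan 2021).

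Neither order is right for all four records.

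**Grid.** First dose was set to each of 365 days from 1 July 2020. True onset was 1–30 days after last dose, in a later calendar month, with the day unknown. For a year-only stop, the true stop was taken as 5 days after onset. The start row was applied first; applying both rows together gives the same shares.

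| Last dose | Records | Stop | Dated on drug | Dated before first dose |
|---|---|---|---|---|
| Day 85 | 5,577 | missing | 100% | 0% |
| Day 85 | 5,577 | year only | 91.5% | 0% |
| Days 2–28 | 150,579 | missing | 31% | 69% |
| Days 2–28 | 150,579 | year only | 28.6% | 62.9% |

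The recorded start is up to 60 days before the true onset. With the stop row first, every share is 0%.

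**Wider denominator.** A simulation took all events 1–28 days after last dose with a month-only onset and missing stop, including onsets in the last-dose month itself. In completers, 47% moved to an earlier month, by a mean of 39 days (range 28–58). The share moved before first dose was 34% for patients stopping on Days 1–28, 43% for Days 7–14, and 0% for completers.

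All these percentages are conditional on the record type. They are not expected frequencies in the trial.

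**The case against.** A reader might infer that the SAP, read in its listed order, records follow-up events as on drug or before first dose. The text does not establish that. In a single pass from top to bottom, the stop is still missing when the start consistency row is reached, so that row cannot fire. The stop is then imputed and moved to the end of the onset month, and records A to C come out correctly. This stands as a possible reading. Against it, the start row refers explicitly to an imputed stop, which presupposes that the stop rows have already run. The single pass also gives the wrong answer for record D.

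Text just before Appendix 3 is redacted, and the contents list other general programming specifications there. An order of operations, or a rule for ongoing events, may be in it. One can say only that no visible text sets the order.

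A reader might also infer a general effect on the primary endpoint. For completers there is none: an onset inside the TEAE window counts whether it is dated on or off drug, and the visible AE summaries do not separate the two. Section 4.3 also keeps data recorded on the case report form in the listings.

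For early stoppers, the clause in 9.2 on undeterminable events leans towards inclusion. It does not clearly cover record C, because the recorded month already shows onset after first dose. Section 9.2 does not say whether the recorded or the imputed date decides.

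**Conclusion.** The point holds as an unresolved conflict between two rows, with a misdated onset under a plausible order. It does not show that the plan necessarily misdates events.

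- **Trigger:** a partial onset whose recorded month or year is after that of the last dose, with a stop that is missing or year-only in the last-dose year, and the start row applied after the stop is imputed. A complete onset date is not moved.
- **Usual effect:** wrong onset day and duration in the listings, with no change in the TEAE count.
- **Worst effect:** a lost TEAE. This also needs first and last dose in one calendar month and a first dose not on the 1st. Doses 84 days apart cannot meet that condition, so 12-week completers are excluded.
- **Size:** the documents give no count of such records. An assumed range is 0–2 in the whole trial, and fewer still in early stoppers. One lost patient would be 1/24 = 4.2 points of overall TEAE incidence in an arm, and only if that event were the patient's sole TEAE.

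This is a low-frequency problem, worth correcting because it touches a primary endpoint and costs little.

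**What to change.** Keep both consistency rows and add to Appendix 3: *An imputed start or stop date never leaves its recorded month or year. If the two estimated dates conflict, move the date with less recorded information (for example, a wholly missing stop yields to a month-and-year onset, and a wholly missing start yields to a month-and-year stop).*

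Under this rule A, B and C keep their onset months and the stop moves to the end of that month. D keeps its February stop and stays before first dose.

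Two simpler remedies should be avoided: limiting the start row to complete stop dates, and always keeping the start date. Either would date record D as 10–31 March, overwriting a recorded stop month and turning a pre-dose event into a TEAE. Stating only that the stop row goes first has the same fault.

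The cost is two sentences in the SAP and a small change to the date-derivation program. If the redacted appendix text already sets an order, it should be checked against records A to D.

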APPENDIX 4. ABBREVIATIONS

| Abbreviation or Special Term | Explanation |
|------------------------------|--|
| 7 α C4 | 7 α -hydroxy-4-cholesten-3-one |
| ADaM | Analysis Data Model |
| AE | adverse event |
| ALP | alkaline phosphatase |
| ALT | alanine transaminase |
| ANCOVA | analysis of covariance |
| AST | aspartate transaminase |
| ATC | Anatomical Therapeutic Class |
| AUC | area under the concentration-time curve |
| BLQ | below limit of quantification |
| BMI | body mass index |
| CAP | Controlled Attenuation Parameter |
| CDISC | Clinical Data Interchange Standards Consortium |
| CHG | change from baseline ADaM basic dataset structure defined variable |
| CI | confidence interval |
| CK-18 | cytokeratin-18 |
| COVID-19 | Coronavirus disease 2019 |
| C _{max} | maximal concentration |
| CRF | case report form |
| CSR | clinical study report |
| CTCAE | Common Terminology Criteria for Adverse Events |
| CTMS | clinical trial management system |
| CV | coefficient of variation |
| DPP-4 | Dipeptidyl peptidase 4 |
| eGFR | estimated glomerular filtration rate |
| eCRF | electronic case report form |
| ECG | electrocardiogram |
| ET | early termination |
| FDA | Food and Drug Administration |
| FGF | fibroblast growth factor |
| FIB-4 | Fibrosis-4 Score |
| FSH | follicle stimulating hormone |
| FXR | farnesoid X receptor |
| GGT | gamma-glutamyl transpeptidase |
| GLP-1 | Glucagon-like peptide-1 |
| HA | hyaluronic acid |
| HDL | high-density lipoprotein |
| hs-CRP | high sensitivity C-reactive protein |
| ICF | informed consent form |
| ICH | International Council for Harmonisation |

| Abbreviation or Special Term | Explanation |
|------------------------------|--|
| IG | implementation guide |
| IMP | investigational medicinal product |
| INR | international normalized ratio |
| IWRS | interactive web response system |
| LDL | low-density lipoprotein |
| LFC | liver fat content |
| LFT | liver function test |
| LLN | lower limit of normal |
| ln | natural log |
| LS | least squares |
| MedDRA | Medical Dictionary for Regulatory Activities |
| MMRM | mixed model for repeated measures |
| MRI-PDFF | Magnetic Resonance Imaging Proton Density Fat Fraction |
| NAFLD | non-alcoholic fatty liver disease |
| NAS | non-alcoholic fatty liver disease activity score |
| NASH | non-alcoholic steatohepatitis |
| NC | not calculated |
| NCA | noncompartmental analysis |
| NCI | National Cancer Institute |
| PCHG | percent change from baseline ADaM basic dataset structure defined variable |
| PIIINP | procollagen III n-terminal propeptide |
| PD | pharmacodynamics |
| PK | pharmacokinetics |
| Pro-C3 | pro-peptide of type III collagen |
| Q1 | 25 th percentile, first quartile |
| Q3 | 75 th percentile, third quartile |
| REML | restricted maximum likelihood |
| SAE | serious adverse event |
| SAP | statistical analysis plan |
| SARS-CoV-2 | severe acute respiratory syndrome coronavirus 2 |
| SD | standard deviation |
| SDG | Standardized Drug Grouping |
| SDTM | Study Data Tabulation Model |
| SE | least squares mean standard error |
| SGLT-2 | Sodium-glucose co-transporter 2 |
| TEAE | treatment emergent adverse event |
| TERN-101 | investigational agonist of Farnesoid X receptor |
| TIMP-1 | tissue inhibitor of metalloproteinases-1 |
| ULN | upper limit of normal |
| WHODD | World Health Organization Drug Dictionary |

APPENDIX 5. DOCUMENT HISTORY

| Version | Date | Author | Description |
|---------|-----------|---|-----------------|
| 1.0 | 19MAY2021 |  | Final Version 1 |

